1 OBJECTIVES

The objective of this study is to assess the following subject matters in patients treated with TORISEL 25 mg Injection (hereinafter called this drug) in post-marketing actual use conditions, thereby providing proper-use information.

- (1) To confirm the effectiveness and safety of this drug under actual use conditions
- (2) To examine the onset state of adverse events and potentially influencing factors (particularly, major investigation items)
- (3) To examine the onset state and potential onset risk factors of interstitial lung disease

[Conditions for approval]

A drug use investigation must be conducted with all the patients treated with this drug until the data from a specified number of cases are accumulated after the marketing of this drug in order to understand the background information on patients treated with this drug, collect the data on the safety and effectiveness of this drug as early as possible, and take necessary measures to ensure the proper-use of this drug.

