6.8 Adverse event

To evaluate safety, the onset of adverse events after the start of the drug administration will be investigated and the following information (1) to (9) will be recorded. In principle, each adverse event will be followed until each safety evaluation date. If an adverse event occurs, the investigator will give appropriate treatment, readily notify the sponsor as specified in the "Adverse Event Reporting" (attachment), and, in principle, follow its outcome and clinical course until its symptom is resolved. Particularly, the investigator will call by phone the following contact number within 24 hours "when a serious adverse event occurs", "when a patient or his/her partner becomes pregnant or is found to be pregnant during the treatment with this drug regardless of the onset of adverse events", or when the investigator knows any additional information on the adverse event or pregnancy. For details, refer to the "Adverse Event Reporting" (attachment).

Contact number in case of serious adverse event

| | |
|------------------|---|
| [TEL] | [name] (toll-free) |
| [Business hours] | 9:00 to 18:00 (available every day of the year) |

In addition, a detailed study will be separately conducted for intrauterine exposure, serious adverse reactions, or adverse reactions not listed in the package insert, etc., if deemed necessary by the sponsor.

- [1] Date of safety evaluation
- [2] Presence/absence of adverse events
- [3] Adverse event name (disease or symptom name)
- [4] Date of onset
- [5] CTCAE v4.0 Grade
- [6] Treatment
- [7] Seriousness
- [8] Current outcome of adverse event
- [9] Causal relationship

Important: Adverse events are any and all unfavorable events (including clinically significant abnormal changes in laboratory tests) occurring in patients after starting the target drug treatment regardless of their causal relationship. Serious adverse events are any unfavorable medical occurrences that result in death, are life-threatening, require (or prolong) hospitalization, cause persistent or significant disability/incapacity, result in congenital anomalies or birth defects, or are other conditions which represent significant health hazards.

Supplementary information:

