7.2 Method of Analysis

7.2.1 Analysis for safety evaluation

The following items will be mainly analyzed in the safety analysis population.

The analytical method for the major investigation items will be specified in the statistical analysis plan, in accordance with the objective of analysis.

- [1] Onset state of adverse events/adverse reactions (particularly the major investigation items)
- [2] Onset state of adverse reactions and potential influencing factors (particularly the major investigation items)
- [3] Safety in patients with special background (pediatric patients, elderly patients, pregnant women, patients with renal or hepatic dysfunction)
- [4] Safety in patients with hepatic dysfunction (including the comparative examination with results from the foreign phase 1 clinical study)
- [5] Onset state of interstitial lung disease (including asymptomatic cases with imaging findings of the disease)
- [6] Potential risk factors of interstitial lung disease
- [7] Characteristics of interstitial lung disease (imaging findings, onset timing, duration, and breakdown by severity)
- [8] List of clinical course of interstitial lung disease (contents of treatment, response to treatment, and outcome) and clinical course after the drug is restarted (presence/absence of recurrence/exacerbation, etc.)
- [9] Onset state of various related events suspected of causing interstitial lung disease (pneumonitis/lung infiltration and pulmonary fibrosis, etc.)

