The number of patients with CTCAE Grade  $\geq 3$  adverse reactions and the incidence of CTCAE Grade  $\geq 3$  adverse reactions will be tabulated by SOC and PT by category shown below. •Further tabulation of serious adverse reactions” will be followed for categories.

- Seriousness;
- Known/unknown;
- Outcome;
- Timing of initial onset;
- Intervention;
- Administration of this drug;
- Duration of treatment;
- Total dose.

- **Further tabulation of adverse events**

The number of patients with adverse events and the incidence of adverse events will be tabulated by SOC and PT by category shown below. “• Further tabulation of serious adverse reactions” will be followed for categories.

- CTCAE Grade.

- **Further tabulation of unknown adverse reactions**

The number of patients with unknown adverse reactions and the incidence of unknown adverse reactions will be tabulated by SOC and PT by category shown below. “•Further tabulation of serious adverse reactions” will be followed for categories.

- Outcome.

- **Cumulative incidence of adverse reactions**

The cumulative incidence of adverse reactions will be graphically presented with the time to onset on the horizontal axis.

The cumulative incidence will be graphically presented in the same manner for interstitial lung disease, diabetes mellitus/hyperglycemia, hypercholesterolemia/hyperlipidemia, infection, mucositis-related adverse events, and skin disorder among major investigation items.

- **Cumulative incidence of CTCAE Grade  $\geq 3$  adverse reactions**

The cumulative incidence of CTCAE Grade  $\geq 3$  adverse reactions will be graphically presented with the time to onset on the horizontal axis.

The cumulative incidence will be graphically presented in the same manner for interstitial lung disease, diabetes mellitus/hyperglycemia, hypercholesterolemia/hyperlipidemia, infection, mucositis-related adverse events, and skin disorder among major investigation items.

- **Incidence of adverse reactions by patient demographic**

The number of patients with adverse reactions and the incidence of adverse reactions will be tabulated by item listed in “[Section 10.1.1. Patient demographics to be used to evaluate safety and efficacy.](#)”

Fisher’s exact test will be performed for nominal scale data and Cochran-Armitage test (exact method) for ordered scale data.

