Tabulation will be performed in the same manner for interstitial lung disease, diabetes mellitus/hyperglycemia, hypercholesterolemia/hyperlipidemia, infection, mucositis-related adverse events, and skin disorder among major investigation items.

For items using reference laboratory test values, results using corporate reference values will be tabulated in addition to results using institutional reference values.

- **Incidence of CTCAE Grade  $\geq 3$  adverse reactions by patient demographic**

The number of patients with CTCAE Grade  $\geq 3$  adverse reactions and the incidence of CTCAE Grade  $\geq 3$  adverse reactions will be tabulated by item listed in “[Section 10.1.1. Patient demographics to be used to evaluate safety and efficacy.](#)”

Tabulation will be performed in the same manner for interstitial lung disease, diabetes mellitus/hyperglycemia, hypercholesterolemia/hyperlipidemia, infection, mucositis-related adverse events, and skin disorder among major investigation items.

For items using reference values, results using corporate reference values will be tabulated in addition to results using institutional reference values.

- **Incidence of adverse reactions by medical history, prior treatment history, and concomitant therapy**

The number of patients with adverse reactions and the incidence of adverse reactions will be tabulated by category shown below.

The number of patients and incidence will be tabulated in the same manner for interstitial lung disease among major investigation items.

- Past medical history;
- Complications;
- Prior medications.

- **Incidence of CTCAE Grade  $\geq 3$  adverse reactions by medical history, prior treatment history, and concomitant therapy**

The number of patients with CTCAE Grade  $\geq 3$  adverse reactions and the incidence of CTCAE Grade  $\geq 3$  adverse reactions will be tabulated by category shown below.

- Past medical history;
- Complications;

- Concomitant medications;
- Non-drug therapies;
- Prior medications.
- **Subgroups**

Safety in the following subgroups will be analyzed.

1. Children (<15 years), adults ( $\geq 15$  years).
2. Elderly ( $\geq 65$  years), non-elderly (<65 years).
3. Presence or absence of pregnancy.
4. Presence or absence of hepatic dysfunction.
5. Presence or absence of renal dysfunction.
6. By indication.
7. By whether criteria for proper use are met.
8. History of hepatitis B, tuberculosis, and herpes zoster.
9. Severity of hepatic dysfunction.
10. Sex.

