11. Complications.

The number of patients with adverse reactions, serious adverse reactions, and CTCAE Grade  $\geq 3$  adverse reactions and the incidence of these adverse reactions will be calculated by SOC and PT.

For items using reference values, results using corporate reference values will be tabulated in addition to results using institutional reference values.

- **Major investigation items**

The number of patients with adverse reactions falling under major investigation items and the incidence of these adverse reactions will be calculated by SOC and PT. The number of patients with adverse events and the incidence of adverse events will be tabulated in the same manner.

The same tabulation will be performed for each of the following items.

1. Interstitial lung disease.
2. A wide range of related events suspected of interstitial lung disease.
3. Dyspnea.
4. Diabetes mellitus/hyperglycemia.
5. Hypersensitivity reaction.
6. Diarrhea.
7. Hypophosphatemia.
8. Hypokalemia.
9. hypercholesterolemia/hyperlipidemia.
10. Infection.
11. Intracerebral hemorrhage.
12. Abnormality in wound healing.
13. Mucositis-related adverse events.
14. Skin disorder.
15. Acute renal failure.
16. Gastrointestinal perforation.

- **Further tabulation of interstitial lung disease**

The number of patients with adverse reactions and adverse events of interstitial lung disease and the incidences of these adverse reactions and adverse events will be tabulated by presence or absence of past or present history of lung disease and presence or absence of abnormal imaging findings at the initiation of treatment by category shown below.

- Seriousness;
- Clinical symptoms;
- Severity (CTCAE Grade);
- Time from the initiation of treatment to initial onset (weeks);
- Cumulative duration (weeks);
- Imaging findings suspected of interstitial lung disease.

The worst CTCAE Grade and treatment effect will be tabulated by presence or absence of treatment of interstitial lung disease.

The outcome in patients in whom interstitial lung disease was CTCAE Grade 1 at onset will be tabulated by status (continued/discontinued) of treatment.

The list of the course of interstitial lung disease and the list of the time course of CTCAE Grade will be prepared.

Graphs of time from the initiation of treatment to initial onset (weeks), outcome, and administration of this drug will be prepared by CTCAE Grade at onset. Graphs will be prepared in the same manner by maximum CTCAE Grade.

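### Objectives 2 and 3 concern adverse events and ILD risk factors of any cause, but apart from one untested ILD table the visible factor analyses count adverse reactions only

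*SAP*

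**What the plan says.** Protocol section 1 sets Objective 2 as "To examine the onset state of adverse events and potentially influencing factors (particularly, major investigation items") and Objective 3 as "To examine the onset state and potential onset risk factors of interstitial lung disease". SAP 2.2.1 repeats both. Protocol 6.8 defines adverse events as those "occurring in patients after starting the target drug treatment regardless of their causal relationship", and the case report form records "Causal relationship" for each event.

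Protocol 7.2.1 item [2] changes the event basis to "Onset state of adverse reactions and potential influencing factors (particularly the major investigation items"), and SAP 6.1 endpoint 2 repeats this. The separate item on potential ILD risk factors (item [6] in Protocol 7.2.1, endpoint 6 in SAP 6.1) has no such limit.

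In SAP 8.2.6, *Incidence of adverse reactions by patient demographic* sets the Section 10.1.1 factors against adverse reactions: "The number of patients with adverse reactions and the incidence of adverse reactions will be tabulated by item listed in" that section. Fisher's exact test or the exact Cochran-Armitage test is applied. For ILD and five other major items: "Tabulation will be performed in the same manner for interstitial lung disease". The Grade 3 or higher tables, the tables by medical history and prior treatment, and the subgroup tables also count adverse reactions only.

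One table differs. *Further tabulation of interstitial lung disease* covers "The number of patients with adverse reactions and adverse events of interstitial lung disease", split by past or present lung disease and by abnormal imaging at the start of treatment. No test is stated for it.

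**The concern.** A causality judgement is made by someone who may know the patient's history. Several factors under study are also natural alternative explanations for a lung event: dust or asbestos exposure, smoking, lung surgery, earlier high-concentration oxygen. If ILD in such patients is more readily called unrelated, the case drops out of the numerator while the patient stays in the denominator. The outcome definition then depends on the exposure, and a real risk factor looks weaker than it is.

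The protocol collects these pulmonary factors specifically, and ILD risk factors are an objective in their own right. A table that shows little association might reflect how events were attributed rather than who developed ILD, and the visible tables would not let a reader tell the two apart.

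**Working it through.** **Which event basis is used where**

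| Place | Event basis | By factor? | Test? |
|---|---|---|---|
| Objective 2 (Protocol 1, SAP 2.2.1) | adverse events | yes | – |
| Objective 3; item [6] / endpoint 6 | ILD, no causality limit | yes | – |
| Protocol 7.2.1 item [2]; SAP 6.1 endpoint 2 | adverse reactions | yes | – |
| SAP 8.2.6, by patient demographic, including ILD | adverse reactions | all of Section 10.1.1 | yes |
| SAP 8.2.6, Grade 3 or higher; medical history; subgroups | adverse reactions | yes | none stated |
| SAP 8.2.6, overall incidence; major items | both | no | – |
| SAP 8.2.6, further tabulation of ILD | both | two factors only | none stated |

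For Objective 2 the narrowing starts in the protocol's own analysis section. For ILD risk factors it appears only in SAP 8.2.6.

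**The plan's figures.** The ILD rate is 14/82 = 17.1%. With 300 patients at 17.1%, the exact binomial probability of at least 40 cases is 0.968, so the plan's statement reproduces. At the target of 600, the expected number is 600 × 0.171 = 102.6 cases. The sample-size rationale does not say whether 17.1% is all-causality; it is taken as such below.

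**Illustration.** From the documents: N = 600, ILD 17.1%, two-sided 5% test. Assumed: factor prevalence 20% (120 against 480 patients), true risk ratio 2.0, and causality ruled out in a share d1 of ILD cases with the factor and d0 = 5% without it.

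- Risk without the factor: 0.171 / (0.8 + 0.2 × 2) = 0.1425. Risk with it: 2 × 0.1425 = 0.285.
- Expected cases: 480 × 0.1425 = 68.4 and 120 × 0.285 = 34.2, together 102.6.
- Observed risk ratio = 2.0 × (1 − d1) / (1 − d0).

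| d1 | d0 | Observed risk ratio | Exact power of Fisher's test |
|---|---|---|---|
| 0 | 0 (all-causality) | 2.00 | 0.93 |
| 5% | 5% | 2.00 | 0.92 |
| 10% | 5% | 2 × 0.90/0.95 = 1.89 | 0.86 |
| 20% | 5% | 2 × 0.80/0.95 = 1.68 | 0.66 |
| 30% | 5% | 2 × 0.70/0.95 = 1.47 | 0.40 |

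Equal loss in both groups leaves the ratio at 2.00 and costs almost no power. The effect comes entirely from the difference between d1 and d0. The observed ratio reaches 1.0 only when 1 − d1 = 0.95/2 = 0.475, that is, when 52.5% of cases with the factor are ruled out.

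**The case against.** **The SAP follows the protocol.** Item [2] in Protocol 7.2.1 already says adverse reactions. This stands for Objective 2: the mismatch lies between the protocol's objectives and its analysis section, and is not a SAP slip alone. It does not cover ILD risk factors, which item [6] leaves unrestricted.

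**The most obvious factors are already handled.** Lung-disease history and baseline imaging, which are perhaps the likeliest grounds for an unrelated judgement, have an all-causality ILD table. This also stands. It would therefore be wrong to infer that the plan analyses only drug-attributed ILD. What is left uncovered is smoking, dust exposure, lung surgery, steroid use, oxygen use and the rest of Section 10.1.1, where differential attribution is more speculative.

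**The attribution rule is not visible.** The text neither defines an adverse reaction nor says whose judgement decides. The listings of deaths in SAP 9 divide them by whether causality was ruled out. If that broad criterion applies throughout, doubtful cases count as reactions and the loss is small.

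**All-causality ILD has its own bias.** In a single-arm study, a factor that raises background lung disease looks like a risk factor even if the drug plays no part. A reader might infer that all-causality ILD should replace the adverse-reaction analysis as the answer to Objective 3. The documents do not support that; each basis has a weakness the other lacks.

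**Redaction and purpose.** Part of SAP 8.2.6 is blacked out and may hold further factor analyses. The study is declared non-confirmatory, so the power figures matter less than the ratios.

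**Conclusion.** The point holds as an objective-to-analysis mismatch. Every visible tested factor analysis of safety uses adverse reactions, while Objective 2 names adverse events and Objective 3 sets no causality limit. Outside the two-factor ILD table, the visible plan cannot show whether attribution has altered an association.

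The size is unknown. Under the stated assumptions, a true ratio of 2.0 would appear as 1.89 to 1.47 when 10% to 30% of cases with the factor are ruled out, against 5% without it. These rates, the prevalence and the true ratio are all assumed. A reader might go further and conclude that the ILD results are biased, or that real risk factors will look protective. Neither follows: the first needs differential attribution, which the documents neither show nor exclude, and the second needs more than half of the cases with the factor to be ruled out in this example.

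**What to change.** 1. In SAP 8.2.6, *Incidence of adverse reactions by patient demographic*, add the same Section 10.1.1 tabulation and tests for all-causality ILD adverse events. Show it beside the adverse-reaction version and declare neither the sole answer to Objective 3.
2. Report, by factor level, the share of ILD events judged unrelated. This shows directly whether attribution differs.
3. Reconcile Objective 2 (adverse events) with Protocol 7.2.1 item [2] and SAP 6.1 endpoint 2 (adverse reactions).
4. Optionally, add an all-causality version for the five other named major items. The mechanism described here is pulmonary, so this is support rather than necessity.

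The cost is SAP wording, a clarification of Objective 2 against the analysis items, and a second run of existing table programs. No new data are needed, because all adverse events and their causality are already recorded under Protocol 6.8. The downside is small: there are more tables to read, and all-causality ILD includes background lung disease, which can dilute an association or create one. That is why the two versions belong side by side.

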2 PATIENTS

This study will be conducted with all patients treated with this drug in a specific period of time. The indications and dosage and administration of this drug are described below.

[Indications]

Metastatic and/or unresectable renal cell carcinoma

[Precautions Regarding Indications]

1. The efficacy and safety of TORISEL as postoperative adjuvant chemotherapy has not been established.
2. The selection of patients in whom to administer TORISEL must be performed after thorough consideration of the efficacy and safety data based on understanding of information detailed in "Clinical Studies*".

* Refer to the [Clinical Studies] section in the package insert.

[Dosage and Administration]

The usual adult dosage is temsirolimus 25 mg once weekly, to be administered via intravenous infusion over 30 - 60 minutes. The dosage is to be appropriately reduced according to patient's condition.

[Precautions regarding dosage and administration]

1. The efficacy and safety of TORISEL in combination use with other anti-malignant tumor agents including cytokine preparations have not been established.
2. When interstitial lung disease occurs, interrupt/discontinue administration depending on the symptoms and severity with consideration of the following criteria:

Criteria for interruption or discontinuation in case of interstitial lung disease

| Symptom | Intervention |
|---|--|
| Asymptomatic. Only abnormal imaging findings are observed. | Continue to administer. |
| Mild clinical symptoms ^{Note)} (not interfering activity of daily living) | Interrupt administration until the symptoms recovered. |
| Severe clinical symptoms ^{Note)} (interfering with activity of daily living and need oxygen therapy) | Discontinue |
| Aggravation of clinical symptoms and pulmonary diffusing capacity decreased | |
| Underlying pulmonary disease, with changes in clinical or image findings are observed | |

Note: Dyspnea, cough, etc.

3. If severe adverse reactions (Grade 3 or severer) occur other than interstitial lung disease, interrupt administration of TORISEL until resolution of the adverse reaction. If the adverse reaction is resolved within 3 weeks, administration can be resumed at a reduced dose by one level (reduction levels should proceed as follows: initial dose 25 mg -> 20 mg-> 15 mg -> 10 mg).

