6.2 Targeted drug use record

The following TORISEL use information will be recorded for each observation period.

- [1] Date of administration
- [2] Dose
- [3] Reason for dose change

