### **8.2.6. Safety Analysis**

- **Incidences of adverse reactions and adverse events**

The number of patients with adverse reactions, serious adverse reactions, adverse events, serious adverse events, and Common Terminology Criteria for Adverse Events (CTCAE) Grade  $\geq 3$  adverse reactions and the incidences of these events will be calculated by system organ class (SOC) and preferred term (PT).

In addition, the number of patients with adverse reactions and the incidence of adverse reactions by inclusion/exclusion from the safety analysis set will be tabulated by SOC and PT in patients for whom the case report form was collected.

- **Further tabulation of adverse reactions**

The number of patients with adverse reactions and the incidence of adverse reactions will be tabulated by SOC and PT by category shown below.

- Seriousness [serious, non-serious];
- Known/unknown [known, unknown];
- Outcome [resolved/recovered, recovering, recovered with sequelae, not recovered];
- Timing of initial onset [ $>0$  to  $\leq 8$  weeks,  $>8$  to  $\leq 16$  weeks,  $>16$  to  $\leq 24$  weeks,  $>24$  to  $\leq 48$  weeks,  $>48$  to  $\leq 72$  weeks,  $>72$  to  $\leq 96$  weeks,  $>96$  weeks];
- Intervention [absent, present];
- Administration of this drug [no change in dose, temporary discontinuation, dose reduction, dose increase, discontinuation];
- Duration of treatment [ $>0$  to  $\leq 8$  weeks,  $>8$  to  $\leq 16$  weeks,  $>16$  to  $\leq 24$  weeks,  $>24$  to  $\leq 48$  weeks,  $>48$  to  $\leq 72$  weeks,  $>72$  to  $\leq 96$  weeks,  $>96$  weeks];
- Total dose [ $>0$  to  $\leq 200$  mg,  $>200$  to  $\leq 400$  mg,  $>400$  to  $\leq 600$  mg,  $>600$  to  $\leq 1200$  mg,  $>1200$  to  $\leq 1800$  mg,  $>1800$  to  $\leq 2400$  mg,  $>2400$  mg];
- CTCAE Grade[Grade 1,Grade 2,Grade 3,Grade 4,Grade 5].

- **Further tabulation of serious adverse reactions**

The number of patients with serious adverse reactions and the incidence of serious adverse reactions will be tabulated by SOC and PT by category shown below. “•Further tabulation of serious adverse reactions” will be followed for categories.

- Known/unknown;
- Outcome;

- Timing of initial onset;
- Intervention;
- Administration of this drug;
- Duration of treatment;
- Total dose;
- CTCAE Grade.

- **Further tabulation of CTCAE Grade  $\geq 3$  adverse reactions**

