- Baseline LDH (1.5-fold of institutional upper reference limit) [high value ( $>1.5$ -fold), normal ( $\leq 1.5$ -fold)];
- Baseline LDH (1.0-fold of institutional upper reference limit) [high value ( $>1.0$ -fold), normal ( $\leq 1.0$ -fold)].

In addition, the above tabulation will be performed using the best overall response as a study not requiring determination of CR and PD.

- Response rate and clinical benefit rate by patient demographic

The response rate and clinical benefit rate will be calculated by item listed in “[Section 10.1.1. Patient demographics to be used to evaluate safety and efficacy.](#)” For the response rate and clinical benefit rate, tests specified in [Section 8.1.3](#) will be performed between categories of each demographic factor.

For items using reference laboratory test values, results using corporate reference values will be tabulated in addition to results using institutional reference values.

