### Nominal scale

Item	Category	Remarks
History of steroid use	Absent, Present	
History of occupational and environmental exposure to asbestos, pneumoconiosis-producing dusts, etc.	Absent, Present	
History of administration of highly concentrated oxygen for treatment of respiratory disease	Absent, Present	
Drug allergies	Absent, Present	
Allergies other than drug allergies	Absent, Present	
Dose at initiation	25 mg, others	
Duration of treatment (weeks)	>0 to ≤8 weeks, >8 to ≤16 weeks, >16 to ≤24 weeks, >24 to ≤48 weeks, >48 to ≤72 weeks, >72 to ≤96 weeks, >96 weeks	No test
Total dose (mg)	>0 to ≤200 mg, >200 to ≤400 mg, >400 to ≤600 mg, >600 to ≤1200 mg, >1200 to ≤1800 mg, >1800 to ≤2400 mg, >2400 mg	No test
Dose intensity (mg/week)	>0 to ≤10 mg, >10 to ≤15 mg, >15 to ≤20 mg, >20 to ≤25 mg, >25 to ≤30 mg, >30 mg	No test
Relative dose intensity	>0.0 to ≤0.4, >0.4 to ≤0.6, >0.6 to ≤0.8, >0.8 to ≤1.0, >1.0 to ≤1.2, >1.2	No test

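### Reactions and response are tabulated by exposure accrued after treatment starts, so the dose-intensity tables can show a false inverse relation with toxicity

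*SAP*

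**What the plan says.** SAP 8.2.6, under incidence by patient demographic, states: "The number of patients with adverse reactions and the incidence of adverse reactions will be tabulated by item listed in" section 10.1.1. It repeats this for Grade ≥3 reactions and for six major investigation items, including interstitial lung disease (ILD). SAP 8.2.7 has the parallel plan: "The response rate and clinical benefit rate will be calculated by item listed in" the same list.

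Most of 10.1.1 is baseline information. Four items are not:

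- duration of treatment;
- total dose, in bands that begin ">0 to ≤200 mg, >200 to ≤400 mg, >400 to ≤600 mg" and end above 2400 mg;
- dose intensity in mg/week, in bands that begin ">0 to ≤10 mg, >10 to ≤15 mg, >15 to ≤20 mg";
- "Relative dose intensity" (RDI).

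All four carry the remark *No test*. Duration and total dose also appear among the categories of the SOC/PT breakdown in 8.2.6: "The number of patients with adverse reactions and the incidence of adverse reactions will be tabulated by SOC and PT by category shown below".

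SAP 6.1 defines duration from first dose to completion of treatment. The visible text gives no window for the other three. The top total-dose edge equals 96 weekly doses (96 × 25 mg = 2400 mg), which matches the top duration edge of 96 weeks and implies the whole course. No visible rule cuts exposure at onset of a reaction.

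Protocol section 2 ties dosing to reactions. A Grade ≥3 reaction other than ILD leads to interruption, and if it resolves in time "administration can be resumed at a reduced dose by one level". Symptomatic ILD leads to interruption or discontinuation. ILD seen only on imaging does not.

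**The concern.** An exposure that the outcome can change is not an influencing factor for that outcome. A patient who has a severe reaction misses doses or continues at a lower level, and so drops to a lower dose-intensity and RDI band because of the reaction. The table then shows more reactions at lower intensity even if dose has no effect on risk.

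Total dose and duration have a second, opposing influence: longer treatment gives more time for a reaction. For response, patients who do not progress stay on drug, and this fills the long-duration and high-total-dose bands with patients who do well.

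These tables serve the second study objective (factors that influence adverse events) and go into the final analysis for re-examination. A reader could take them as evidence on dose and toxicity.

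**Working it through.** **The plan's own figure.** The documents give none for these tables. The sample-size rationale reproduces (1 − 0.99^300 = 0.951), but nothing below depends on it.

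**Mechanism for one patient.** Take RDI as (total dose ÷ weeks) ÷ 25; the SAP gives no formula. Without a reaction, 12 weekly doses of 25 mg give 300 mg, 25 mg/week and RDI 1.0. If a patient reacts after dose 4, misses 2 doses and receives 20 mg for the last 6 weeks, the total is 4 × 25 + 6 × 20 = 220 mg. That is 220/12 = 18.3 mg/week and RDI 0.73. Up to onset both patients have RDI 1.0.

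**Simulation with no dose effect.** There were 30,000 patients per scenario, dosed weekly for up to 96 weeks.

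- From the documents: ILD 17.1% and 12-week continuation of 50–60% (Protocol section 3); resumption one level lower (Protocol section 2).
- Assumed: an alternative reaction risk of 50%; 20% or 50% of reactors stop; the others miss 1–3 doses and continue one level lower; onset hazard constant or confined to Weeks 1–8; 20% of patients on a lower dose for unrelated reasons.

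Incidence by RDI band (>0.6–0.8 vs >0.8–1.0):

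| Scenario | Whole course | Ratio | Cut at first onset |
|---|---|---|---|
| ILD-type, constant hazard, 50% stop | 17.8% vs 10.3% | 1.73 | 12.7% vs 12.3% |
| 50% reaction, constant hazard, 20% stop | 50.2% vs 25.4% | 1.98 | 33.8% vs 34.3% |
| 50% reaction, early onset, 50% stop | 60.8% vs 30.0% | 2.03 | 42.0% vs 42.3% |

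A second simulation, also with 20% unrelated lower dosing, gave 44% vs 25% at a hazard of 3% per week (ratio 1.76) and 27% vs 14% at 1.5% per week (ratio 1.93). Both became flat when exposure was cut at onset.

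**Where the gap comes from (row 2).**

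- Cut at onset, the lower band holds 6048 patients: 6048 × 0.338 ≈ 2044 reactors and 4004 non-reactors.
- Over the whole course it holds 8043: 8043 × 0.502 ≈ 4038 reactors and 4005 non-reactors.
- In the upper band, reactors fall from 23952 × 0.343 ≈ 8216 to 21082 × 0.254 ≈ 5355.

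The non-reactors stay where they were. Only the reactors move down.

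**First-onset rates per 100 person-weeks by current dose (20 vs 25 mg), same three scenarios.** 0.81 vs 0.78, 2.77 vs 2.83 and 3.93 vs 3.99. All are flat, as they should be.

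**Total dose and duration, no dose effect, no unrelated lower dosing.**

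- Total dose, early onset: ILD-type falls from 22.9% (≤200 mg) to 3.4% (>1800–2400 mg); 50% reaction with half stopping falls from 52.1% to 14.7%.
- Total dose, constant hazard: ILD-type rises from 8.5% to 26.9%.
- Duration: ILD-type with early onset is 21.5% at ≤8 weeks against 9–11% later; with constant hazard it rises from 7.8% to 35.7%; 50% reaction with early onset and 20% stopping is about flat (43–46%).

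**The case against.** The strongest reply is that the SAP already treats these items with caution. All four are marked *No test*, and section 4 says the study is not confirmatory. Dose at initiation (25 mg or other) stands in the same list, is fixed before any reaction and has no such remark. The SAP also plans action taken with the drug, timing of first onset, cumulative incidence over time, and reasons for interruption and dose reduction. Part of 8.2.6 is redacted, so an onset-limited exposure analysis there cannot be excluded.

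Much of this stands as mitigation. No false p-value arises, and a careful reader has some context. But *No test* removes only the p-value and leaves the incidences. The starting-dose comparison is sound but coarse and does not correct the other tables. None of the visible analyses relates risk to dose before onset. A redacted analysis would not change the tables that are visible.

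A reader might infer more than the documents support:

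- **Reactions in 100% of patients with reduced RDI.** This follows only if nobody but reactors can have a reduced dose, so it is built into that assumption. Low-grade reactions need not change dosing, and doses are reduced for other reasons too.
- **A false inverse relation for all four exposures.** For total dose and duration the direction depends on onset timing and on how often reactors stop.
- **Fewer responses at lower dose intensity.** Longer treatment also gives more time for dose reductions. With no dose effect, 10% responders, weekly off-drug hazards of 2% (responders) and 8% (others), and a 5% weekly chance of a dose step-down in both, response was 27% in RDI >0.6–0.8 and 6.8% in >0.8–1.0, the opposite direction.

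**Conclusion.** The point holds for descriptive tables. As planned, the dose-intensity and RDI tables can show a false inverse relation with toxicity, mainly for Grade ≥3 reactions and symptomatic ILD. With no true dose effect and 20% unrelated lower dosing, the false ratio between the two main RDI bands is about 1.7 to 2.0. Its size depends on the assumed hazard, stopping rate and share of unrelated lower dosing, so the figures are illustrative.

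For total dose and duration the tables are biased in a direction that cannot be predicted. For response, total dose and duration lean towards a false positive relation. No direction is claimed for response by dose intensity or RDI.

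The whole-course window is explicit only for duration. For the other three it is inferred from the bands, so the documented gap there is an undefined window.

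**What to change.** 1. In SAP 8.2.6 and 10.1.1, define the exposure window. For the reaction tables, compute dose intensity and RDI only up to first onset of the event being tabulated. Include the dose given on or just before onset, so that reactions on the first dosing day are defined.
2. Replace incidence by total dose and duration with first-onset rates per cumulative-dose or time band, among patients still event-free and on drug. State how onsets in the 28 days after the last dose (Protocol 5.4) are assigned.
3. In 8.2.7, use exposure up to a Week 8 landmark, among patients whose tumour was evaluated then.
4. Keep whole-course exposure as description in 8.2.5, labelled as not interpretable as dose-response.

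No new data are needed. Protocol 6.2 records the date and dose of each administration and "Reason for dose change", and Protocol 6.8 records the onset date. The cost is SAP wording, some programming and smaller denominators in late bands.

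Two limits remain. The change removes reverse causation but not confounding, such as frailer patients receiving lower doses. Also, if unrelated reductions accumulate over time, RDI up to onset covers a shorter window in reactors than in others; first-onset rates by current dose avoid this and are a useful companion table.
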